All patients in the study will be undergoing non-urgent surgery at Wake Forest University Baptist Medical Center. The interventions will be performed in the regional anesthesia area of the surgery center. Patients will remain in the hospital at least one night, and once discharged, all patients will have daily follow-up by phone with the regional anesthesia acute pain management team.

Subject selection criteria

Patients undergoing non-urgent unilateral ankle arthrodesis or open reduction and internal fixation of bi/tri malleolar fractures will be recruited for the study.

- Inclusion Criteria**

Patients will be eligible for inclusion in the study if they are between the ages of 18-75 and are scheduled to undergo unilateral ankle arthrodesis or open reduction and internal fixation of bi/tri malleolar fractures at Wake Forest University Baptist Medical Center. Patient must give written informed consent for anesthesia including continuous sciatic nerve block and saphenous block for postoperative analgesia prior to recruitment. Patients must be able to comprehend the use and care of the catheters and infusion pump systems both in the hospital, and at once discharged home with verbal and written instructions

- Exclusion Criteria**

Patients will be excluded if they have a contraindication to saphenous or sciatic nerve blockade (including significant coagulation abnormalities), history of opioid addiction, current chronic pain therapy with high-dose opioid (extended release opioids or > 40mg oxycodone equivalents per day), allergy to study medications, or failure to place a sciatic catheter. Failure to achieve successful sciatic analgesia or a successful primary saphenous block will also lead to exclusion.

- Sample Size**

74 patients will be recruited for the study and will be randomized into two groups of $n = 37$ patients each. This sample size provides power = 0.80 to allow reliable detection of group differences of $d = 0.74$ standard deviation units (approximately 1.5 points on a 0 -10 pain scale in our pilot data), assuming two-sided inferences held to the $\alpha =$

0.025 level (see stats section for details on error control). Differences smaller than this magnitude are unlikely to be clinically meaningful.

Interventions and Interactions

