Patients will be generally discharged home with peripheral nerve catheters in place on POD #1, after receiving written and verbal instructions in perineural catheter management. These patients will be called at 24 and 48 hours post discharge to determine rest and incident numeric pain scores, opioid usage, sleep quality (as number of awakenings for pain), and the presence of nausea or vomiting. Patients will be given contact numbers and instructions to call with any questions or concerns per usual practice.

Outcome Measure(s)

The primary endpoint of this study will be a reduction of the rest and incident verbal pain scores 48hpost-nerve blockade when the primary saphenous single-shot block is expected to have resolved. Secondary endpoints of reduction of opioid use, nausea and vomiting, sleep disturbance (as number of awakenings), and reduction of quadriceps strength will also be evaluated. Additionally, we will describe an ultrasound guided technique for placement of a continuous saphenous nerve catheter supported by cadaveric dissection.

Analytical Plan

All analyses will be conducted with SAS 9.2 (SAS, Inc., Cary, NC). Prior to conducting the primary analysis, the distributional characteristics of all variables will be considered by examining histograms and descriptive statistics. Where possible, all analyses will be conducted using the general linear model (e.g., t-test), but where necessary nonparametric equivalents will be conducted for pairwise comparisons (e.g., Mann-Whitney U). As a result of random assignment, participant characteristics are expected to be similar, but treatment group characteristics will be compared using descriptive statistics. The primary analysis will consist of a direct comparison between treatment groups at 48 hours using an independent t-test. Because the primary analysis consists of two comparisons (i.e., pain with rest and pain with movement), each comparison will be evaluated at the $\alpha = 0.025$ level (i.e., holding the family to a conservative 5% type-I error rate). Secondary analyses will be conducted using tests appropriate for the level of measurement including t-tests, Mann-Whitney U (ordinal data such as number of awakenings), and χ^2 (categorical data such as presence of nausea). Statistical significance for all secondary comparisons will be interpreted at $p < 0.05$. No interim analyses will be conducted.

Human Subjects Protection

Informed Consent

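### Testing each of the two primary pain scores at a fixed 0.025 is valid, but Holm's step-down test gives more power for the second score at the same 5% family-wise error and the same N

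*Combined protocol and SAP*

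**What the plan says.** The Outcome Measure(s) section gives the primary endpoint as "a reduction of the rest and incident verbal pain scores" 48 hours after the block, so rest pain and movement pain are both primary, with no order between them. The Analytical Plan compares the groups by independent t-test and sets the error rule: "Because the primary analysis consists of two comparisons (i.e., pain with rest and pain with movement), each comparison will be evaluated at the" 0.025 level, described as "holding the family to a conservative 5% type-I error rate".

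The Sample Size section uses the same level. "74 patients will be recruited for the study and will be randomized into two groups of" 37 each. "This sample size provides power = 0.80 to allow reliable detection of group differences of" 0.74 "standard deviation units (approximately 1.5 points on a 0 -10 pain scale in our pilot data"), "assuming two-sided inferences held to the" 0.025 level. It adds: "Differences smaller than this magnitude are unlikely to be clinically meaningful".

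The Analytical Plan excludes interim analyses, so no other look at the data draws on the primary error rate. Neither section contains a step-down, hierarchical or gatekeeping rule.

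**The concern.** Plain Bonferroni keeps the second score at 0.025 even after the first has been shown significant. At that point only one hypothesis is left, and it can be tested at the full 0.05 without taking the family above 5%. The fixed split therefore gives up power that the plan's own error target allows.

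Take p = 0.010 on one score and p = 0.040 on the other. The planned rule declares the first significant and not the second. Holm declares both, at the same family-wise error. Since the endpoint names both scores, the result on the second affects what the trial can conclude. Here the second score means the one with the larger p-value, not a score named in advance.

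**Working it through.** **Inputs from the documents:** 37 per arm; d = 0.74 SD, about 1.5 points; two-sided 0.025 per score; stated power 0.80; independent t-test; two primary scores.

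**Assumed:** correlation ρ between the two scores of 0.3 to 0.8 (the documents give none); the same d on both scores; normally distributed scores.

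**1. The plan's own figure.** Degrees of freedom are 2 × 37 − 2 = 72. The noncentrality is d√(n/2) = 0.74 × √18.5 = 3.18. The two-sided critical value at 0.025 is t = 2.289. Noncentral-t power is 0.812, and 37 is the smallest n per arm that reaches 0.80. The stated figure reproduces.

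**2. Validity of the planned rule.** 0.025 + 0.025 = 0.05, which bounds the family-wise error under any correlation.

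**3. What Holm changes.** Order the p-values. Reject the smaller if it is ≤ 0.025; if so, reject the larger if it is ≤ 0.05. The two rules differ only when one p-value is ≤ 0.025 and the other lies between 0.025 and 0.05. Once the first score is rejected, the second faces a 0.05 test, whose nominal power at d = 0.74 is 0.881 against 0.812 at 0.025.

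**4. Power by simulation** (200,000 trials per scenario, bivariate normal, pooled t-tests, 37 per arm, d = 0.74 on both scores):

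| ρ | Each score, planned | Each score, Holm | Both, planned | Both, Holm | At least one, either rule |
|---|---|---|---|---|---|
| 0.3 | 0.81 | 0.862 | 0.682 | 0.783 | 0.941 |
| 0.5 | 0.81 | 0.859 | 0.703 | 0.796 | 0.922 |
| 0.7 | 0.81 | 0.855 | 0.729 | 0.812 | 0.899 |
| 0.8 | 0.81 | 0.851 | 0.744 | 0.820 | 0.882 |

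Consistency check: with equal effects, per-score power is the mean of the at-least-one and both columns. At ρ = 0.5 under Holm, (0.922 + 0.796)/2 = 0.859.

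**5. The gain in patients.** For the planned rule to give about the same both-score power it would need 44 per arm at ρ = 0.3 (0.791) and ρ = 0.5 (0.802), and 43 per arm at ρ = 0.7 (0.809) and ρ = 0.8 (0.819). That is 86 to 88 patients against 74. This is only an equivalence; the planned N meets its own per-score target.

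**6. Error rates.** With both scores null, the chance of any rejection is the same under the two rules: 0.049, 0.046, 0.043 and 0.040 at ρ = 0.3, 0.5, 0.7 and 0.8. With d = 0.74 on one score and 0 on the other, the null score is falsely rejected with probability 0.025 under the planned rule and 0.044, 0.044, 0.041 and 0.039 under Holm, still below 0.05.

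**7. Size of the added rejections.** The implied SD is 1.5/0.74 = 2.03 points, and the standard error of the difference is 2.03 × √(2/37) = 0.471. The critical difference at p = 0.025 is 2.289 × 0.471 = 1.08 points (0.53 SD); at p = 0.05 it is 1.993 × 0.471 = 0.94 points (0.46 SD). Every added rejection has an observed difference in that band.

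**8. Intervals.** At p = 0.040, t = 2.092 and the difference is 2.092 × 0.471 = 0.99 points. The 95% interval is 0.05 to 1.93. The 97.5% interval is −0.09 to 2.06, which includes zero although Holm may reject.

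**The case against.** The strongest reply is that nothing here is defective. The split was chosen deliberately, is called conservative in the plan, and matches the sample-size calculation, which is met with power to spare. That stands, and it is why this is an improvement and not an error.

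Second, splitting alpha implies that either score can carry the trial, and for at least one significant score Holm adds nothing. If instead both scores had to be significant, no split would be needed: each at 0.05 gives both-score power of 0.79–0.83, about 0.01 above Holm. That is also correct. Holm helps where a separate claim is wanted on each score, which is what two tests each with its own significance level provide. On that basis the gain is 4 to 5 percentage points per score.

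Third, the added rejections have observed differences of 0.94 to 1.08 points, below the 1.5 points the plan treats as meaningful. This limits their value. But the planned rule already rejects from 1.08 points upward, and at p = 0.040 the 95% interval reaches 1.93, so 1.5 points is not excluded.

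Fourth, false rejection of a null score becomes more likely when the other effect is real, and the directly matching 97.5% intervals are lost. Both costs are real. The first stays within the plan's 5% target, and the second can be handled in reporting.

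Finally, the sizes depend on assumptions. The Sample Size section does not say whether its pilot effect is for rest or movement, and the Analytical Plan allows Mann–Whitney tests where needed. The exact gains are therefore conditional, but Holm's advantage in rejections is not: it works on valid p-values from either test.

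**Conclusion.** The point holds as a low-cost improvement. The fixed 0.025 rule is valid and consistent with 37 per arm. Holm rejects everything that rule rejects and more, with family-wise error at or below 5% whatever the correlation. With d = 0.74 on both scores, normal data and an assumed correlation of 0.3 to 0.8, the gain is about 0.04–0.05 in power per score and about 0.08–0.10 in power to show both. That Holm rejects at least as much at the same family-wise error is certain; the size of the gain depends on the assumed correlation and on equal effects.

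**What to change.** Before unblinding, replace the fixed-level sentence in the Analytical Plan with: *The two primary p-values (rest and movement pain at 48 hours) will be tested by Holm's procedure: the smaller at 0.025 and, if significant, the larger at 0.05.* Add a reporting sentence: *Holm-adjusted p-values will be given, with 95% confidence intervals labelled as unadjusted.* Significance should not be read from 97.5% intervals, because these can include zero when Holm rejects. Each estimate and interval should be read against the 1.5-point difference alongside its p-value.

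The cost is two sentences. N stays at 74, and the per-score calculation at 0.025 can stay as a conservative basis for the sample size.

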Appendix

1. Data collection form
2. Consent form
